## Appendix 2. Clinical Laboratory Tests

---

**Hematologya,b**

Hemoglobin  
 Hematocrit  
 Erythrocyte count (RBC)  
 Mean cell volume (MCV)  
 Mean cell hemoglobin concentration (MCHC)  
 Leukocytes (WBC)  
 Platelets

**Absolute counts of:**

Neutrophils, segmented  
 Neutrophils, juvenile (bands)  
 Lymphocytes  
 Monocytes  
 Eosinophils  
 Basophils

**Urinalysis (dipstick)a,b**

color  
 Specific gravity  
 pH  
 Protein  
 Glucoseg  
 Ketones  
 Bilirubin  
 Urobilinogen  
 Blood  
 Nitrite  
 Urine creatinine  
 Leukocyte esterase  
 Urinalysis (microscopic):  
 Sediment, cells, casts

**Other Testsa**

Human immunodeficiency virus antibody (HIV)c,d  
 Hepatitis B Surface antigen (HBsAg)c,d  
 Anti-Hepatitis B Core antibody (HBcAb)c,d  
 Anti-Hepatitis B Surface antibody (HBsAb)d  
 Anti-Hepatitis C antibodyc,d  
 HBV DNAc,d

Tuberculosisd

**Serum Chemistrya,b**

Sodium  
 Potassium  
 Bicarbonate  
 Chloride  
 Phosphorus  
 Total bilirubin  
 Direct bilirubin  
 Alkaline phosphatase  
 Alanine aminotransferase (ALT/SGPT)  
 Aspartate aminotransferase (AST/SGOT)  
 Blood urea nitrogen (BUN)  
 Uric acid  
 Creatinine  
 Calcium  
 Glucoseg  
 Albumin  
 Cholesterol (total)  
 Total protein  
 CPK  
 Triglycerides  
 Gamma-Glutamyl Transferase (GGT)

**Immunogenicity**

Ixekizumab serum concentration

Pregnancy Test (serum and urine)e  
 Follicle stimulating hormone (FSH)d,f

**Clinical Safety Laboratory Tests**

Abbreviations: CPK = creatine phosphokinase; DNA = deoxyribonucleic acid; HBV = hepatitis B virus; RBC = red blood cells; SGOT = serum glutamic oxaloacetic transaminase; SGPT = serum glutamic pyruvic transaminase; WBC = white blood cells.

- a Assayed by sponsor-designated laboratory.
- b Unscheduled blood chemistry, urinalysis, and hematology panels may be performed at the discretion of the investigator.
- c See exclusion criteria (Section 6.2).
- d Test required at Visit 1 only to determine eligibility of patient for the study (note: with the exception of those patients who require further HBV monitoring [Section 9.4.6.3]).
- e Serum pregnancy test (women <60 years of age who are still of childbearing potential) and urine pregnancy test (women of childbearing potential). Patients will undergo urine pregnancy self-testing at home on a monthly basis during periods between scheduled visits until Week 24. During these intervisit periods, the site must call the patient each month to obtain her pregnancy test results. Additional urine pregnancy testing can be performed at the investigator's discretion. Patients determined to be pregnant will be discontinued from treatment and will no longer be administered study drug (see Section 8.1.1).
- f Women  $\geq 40$  and <60 years of age who have had a cessation of menses for  $\geq 12$  months will have an FSH test confirming nonchildbearing potential ( $\geq 40$  mIU/mL). FSH test will be performed centrally.
- g non-fasting glucose.

---

**Appendix 3. Study Governance Considerations**

---

## **Appendix 3.1. Regulatory and Ethical Considerations, Including the Informed Consent Process**

### ***Appendix 3.1.1. Informed Consent***

The investigator is responsible for:

- ensuring that the patient understands the nature of the study, the potential risks and benefits of participating in the study, and that their participation is voluntary.
- ensuring that informed consent is given by each patient or legal representative. This includes obtaining the appropriate signatures and dates on the informed consent form (ICF) prior to the performance of any protocol procedures and prior to the administration of study drug.
- answering any questions the patient/may have throughout the study and sharing in a timely manner any new information that may be relevant to the patients willingness to continue his or her participation in the study.
- ensuring that a copy of the ICF is provided to the participant or the participant's legal representative and is kept on file.
- ensuring that the medical record includes a statement that written informed consent was obtained before the participant was enrolled in the study and the date the written consent was obtained. The authorized person obtaining the informed consent must also sign the ICF.

### ***Appendix 3.1.2. Recruitment***

Lilly or its designee is responsible for the central recruitment strategy for patients. Individual investigators may have additional local requirements or processes.

### ***Appendix 3.1.3. Ethical Review***

The investigator must give assurance that the ethical review board (ERB) was properly constituted and convened as required by International Council for Harmonisation (ICH) guidelines and other applicable laws and regulations.

Documentation of ERB approval of the protocol and the ICF must be provided to Lilly before the study may begin at the investigative site(s). Lilly or its representatives must approve the ICF, including any changes made by the ERBs, before it is used at the investigative site(s). All ICFs must be compliant with the ICH guideline on Good Clinical Practice (GCP).

The study site's ERB(s) should be provided with the following:

- the protocol and related amendments and addenda, current Investigator Brochure (IB) and updates during the course of the study
- informed consent form
- other relevant documents (e.g., curricula vitae, advertisements)

**Appendix 3.1.4. Regulatory Considerations**

This study will be conducted in accordance with the protocol and with the:

- consensus ethics principles derived from international ethics guidelines, including the Declaration of Helsinki and Council for International Organizations of Medical Sciences (CIOMS) International Ethical Guidelines
- applicable ICH GCP Guidelines
- applicable laws and regulations

Some of the obligations of the sponsor will be assigned to a third party.

**Appendix 3.1.5. Investigator Information**

Physicians with a specialty in dermatology or other relevant specialties with appropriate experience in diagnosis and treatment of patients with psoriasis will participate as investigators in this clinical trial.

**Appendix 3.1.6. Protocol Signatures**

The sponsor's responsible medical officer will approve the protocol, confirming that, to the best of his or her knowledge, the protocol accurately describes the planned design and conduct of the study.

After reading the protocol, each principal investigator will sign the protocol signature page and send a copy of the signed page to a Lilly representative.

**Appendix 3.1.7. Final Report Signature**

The investigator will sign the final clinical study report (CSR) for this study, indicating agreement with the analyses, results, and conclusions of the report.

The CSR coordinating investigator will sign the final CSR for this study, indicating agreement that, to the best of his or her knowledge, the report accurately describes the conduct and results of the study.

The investigator with the most analyzable and enrolled patients will serve as the CSR coordinating investigator. If this investigator is unable to fulfill this function, another investigator will be chosen by Lilly to serve as the CSR coordinating investigator.

The sponsor's responsible medical officer and statistician will approve the final CSR for this study, confirming that to the best of his or her knowledge, the report accurately describes the conduct and results of the study.

## Appendix 3.2. Data Quality Assurance

To ensure accurate, complete, and reliable data, Lilly or its representatives will do the following:

- provide instructional material to the study sites, as appropriate
- provide sponsor start-up training to instruct the investigators and study coordinators. This training will give instruction on the protocol, the completion of the CRFs, and study procedures
- make periodic visits to the study site
- be available for consultation and stay in contact with the study site personnel by mail, telephone, and/or fax
- review and verify data reported to detect potential errors

In addition, Lilly or its representatives will periodically check a sample of the patient data recorded against source documents at the study site. The study may be audited by Lilly or its representatives and/or regulatory agencies at any time. Investigators will be given notice before an audit occurs.

The investigator will keep records of all original source data. This might include laboratory tests, medical records, and clinical notes. If requested, the investigator will provide the sponsor, applicable regulatory agencies, and applicable ERBs with direct access to original source documents.

### **Appendix 3.2.1. Data Capture System**

The investigator is responsible for ensuring the accuracy, completeness, legibility, and timeliness of the data reported to the sponsor.

An electronic data capture (EDC) system will be used in this study for the collection of CRF data. The investigator maintains a separate source for the data entered by the investigator or designee into the sponsor-provided EDC system. The investigator is responsible for the identification of any data to be considered source and for the confirmation that data reported are accurate and complete by signing the CRF.

Clinical outcome assessment (COA) data (questionnaires) will be collected by the investigator site personnel from the patient, via a paper source document and will be transcribed by the investigator site personnel into the EDC system.

Additionally, electronic Clinical Outcome Assessment (eCOA) data (questionnaires, scales, rating scales etc.) will be directly recorded by the subject/investigator site personnel, into an instrument (e.g., hand held tablet). The eCOA data will serve as the source documentation and the investigator does not maintain a separate, written or electronic record of these data.

Data collected via the sponsor-provided data capture system(s) will be stored at a third-party site. The investigator will have continuous access to the data during the study and until decommissioning of the data capture system(s). Prior to decommissioning, the investigator will receive an archival copy of pertinent data for retention.

Data managed by a central vendor, such as laboratory test data, will be stored electronically in the central vendor's database system and electronic transfers will be provided to the investigator for review and retention. Data will subsequently be transferred from the central vendor to the Lilly Clinical Laboratory Results Modernization database.

Data from complaint forms submitted to Lilly will be encoded and stored in the global product complaint management system.

### **Appendix 3.3. Study and Site Closure**

#### ***Appendix 3.3.1. Discontinuation of Study Sites***

Study site participation may be discontinued if Lilly, the investigator, or the ERB of the study site judges it necessary for medical, safety, regulatory, or other reasons consistent with applicable laws, regulations, and GCP.

#### ***Appendix 3.3.2. Discontinuation of the Study***

The study will be discontinued if Lilly judges it necessary for medical, safety, regulatory, or other reasons consistent with applicable laws, regulations, and GCP.

#### ***Appendix 3.4. Publication Policy***

The publication policy for Study IIF-MC-RHCR is described in the letters of agreement between the Sponsor and the investigators and institutions.

---

## Appendix 4. Hepatic Monitoring Tests for Treatment-Emergent Abnormality

---

Selected tests may be obtained in the event of a treatment-emergent hepatic abnormality and may be required in follow-up with patients in consultation with the Lilly, or its designee, clinical research physician.

### Hepatic Monitoring Tests

---

#### Hepatic Hematologya

Hemoglobin  
Hematocrit  
RBC  
WBC  
Neutrophils, segmented  
Lymphocytes  
Monocytes  
Eosinophils  
Basophils  
Platelets

#### Hepatic Chemistrya

Total bilirubin  
Direct bilirubin  
Alkaline phosphatase  
ALT  
AST  
  
GGT  
CPK

#### Haptoglobina

#### Hepatic Serologiesa,b

Hepatitis A antibody, total  
Hepatitis A antibody, IgM  
Hepatitis B surface antigen  
Hepatitis B surface antibody  
Hepatitis B Core antibody  
Hepatitis C antibody  
Hepatitis E antibody, IgG  
Hepatitis E antibody, IgM

#### Anti-nuclear antibodya

#### Alkaline Phosphatase Isoenzymesa

#### Anti-smooth muscle antibody (or anti-actin antibody)a

---

Abbreviations: ALT = alanine aminotransferase; AST = aspartate aminotransferase; CPK = creatinine phosphokinase; GGT = gamma-glutamyl transferase; Ig = immunoglobulin; RBC = red blood cells; WBC = white blood cells.

a Assayed by Lilly-designated or local laboratory.

b Reflex/confirmation dependent on regulatory requirements and/or testing availability.

---

**Appendix 5. Protocol Amendment I1F-MC-RHCR(b)  
Summary: A 24 Week Multicenter, Randomized, Double  
Blind, Parallel Group Study Comparing the Efficacy and  
Safety of Ixekizumab to Guselkumab in Patients with  
Moderate to Severe Plaque Psoriasis**

---

## **Overview**

Protocol I1F-MC-RHCR(a) A 24 Week Multicenter, Randomized, Double Blind, Parallel Group Study Comparing the Efficacy and Safety of Ixekizumab to Guselkumab in Patients with Moderate to Severe Plaque Psoriasis has been amended. The new protocol is indicated by amendment (b) and will be used to conduct the study in place of any preceding version of the protocol.

The overall changes and rationale for the changes made to this protocol are described in the following table:

**Amendment Summary for Protocol I1F-MC-RHCR Amendment (b)**

Section # and Name	Description of Change	Brief Rationale
5.1 Overall Design	Added the following clarification to “the other appropriate means” of patient blinding by the Unblinded Site Personnel: “physical barrier means communicated to the sponsor for final approval.”	Improve clarity
5.2 Number of Participants	Rephrased 1 st sentence of the 2 nd paragraph and replaced “treatment with” with “exposure to” in the last sentence of the 2 nd paragraph.	Improve clarity
6.2 Exclusion Criteria	Exclusion criteria # [15] Removed the restriction of participation in any study investigating other IL-17 antagonists.	Based on recent protocol review and feedback received, a decision was made to be consistent regarding the current or recent use of other IL-17 antagonists. This amendment is to be consistent with the eligible population despite of the source of the exposure. Prior exposure to other IL-17 antagonist in clinical trial settings will be allowed as long as all other inclusion/exclusion criteria are respected; especially > 5 half-lives washout period before baseline visit (Week 0, Visit 2). As specified in Section 5.2 of the protocol, the patient population with previous exposure to another IL-17 antagonist(s) will be limited to approximately 15% of the total patient population.

Section # and Name	Description of Change	Brief Rationale
6.2 Exclusion Criteria	
Exclusion criteria # [22]                      Added the following clarifications:                      “except for basal cell carcinoma, squamous cell carcinoma, skin Bowen’s disease or actinic keratosis that have been treated with no evidence of recurrence in the past 12 weeks or carcinoma in situ of the cervix or non-invasive malignant colon polyps that have been removed.”
	
This addition is to clarify that subjects with the types of non-invasive malignancies and Non-Melanoma Skin Cancers (NMSC), as described in the clarification, can be included in this study, if they have been successfully treated with no evidence of recurrence. This is similar to other biologicals psoriasis studies and aligned with both products labels. In Lilly’s opinion, including such patients in this short study (24 weeks of active treatment periods) will not pose an increased risk of such events since similar populations have previously participated in other biological psoriasis studies.

6.2.1 Rationale for Exclusion of Certain Study Candidates	
Removed IL-17 antagonist from the description of exclusion criteria and editorial changes.
	
For content consistency as a result of changes made to Exclusion Criteria #[15].

7.8 Concomitant Therapy	
Table RHCR.7.3                      Drug Class “IL 17, IL-23p19 antagonists, other than the 2 products used as part of this protocol”:                      Removed IL-17 and replaced “treatment with” with “exposure to” in the description of Condition for Use.
	
For content consistency as a result of changes made to Exclusion Criteria #[15] and improve clarity.

## Revised Protocol Sections

Note: Deletions have been identified by <del>strikethroughs</del> . Additions have been identified by the use of underscore .
--

### 5.1. Overall Design

Unblinded Site Personnel are also responsible for maintaining the blind of the patient (e.g., by means of a blindfold or other appropriate physical barrier means communicated to the sponsor for final approval).

### 5.2. Number of Participants

Patients with previous biologic use (~~note: except concurrent or recent use of any biologic agent < 5 half-lives~~) will be can be included in the study provided all inclusion/exclusion criteria, including the washout period(s), as specified in (see Sections 6.1 and 6.2)-of this protocol are respected. Patients with previous ~~treatment with~~ exposure to another IL-17 antagonist(s) will be limited to approximately 15% of the total patient population.

### 6.2. Exclusion Criteria

- [15] Have previously completed or withdrawn from this study, participated in any other study with ixekizumab or guselkumab, have participated in any study investigating ~~other IL-17 or~~ IL-23p19 antagonists, or have received treatment with ixekizumab.
- [22] Have current or a history of lymphoproliferative disease, or signs or symptoms of lymphoproliferative disease within 5 years of baseline (Week 0, Visit 2); or have active or history of malignant disease within 5 years of baseline (Week 0, Visit 2), except for basal cell carcinoma, squamous cell carcinoma, skin Bowen's disease or actinic keratoses that have been treated with no evidence of recurrence in the past 12 weeks or carcinoma in situ of the cervix or non-invasive malignant colon polyps that have been removed.

(Note: patients with history of malignancy with no evidence of recurrence or active disease within 5 years of baseline may participate in the study).

#### 6.2.1 Rationale for Exclusion of Certain Study Candidates

Exclusion Criteria [12] through [16] exclude patients who have prior exposure to: guselkumab, or any IL-23p19 antagonist, or ixekizumab or any IL-17 antagonist (note: see details in Sections 6.2 and 5.2), or any patients who are receiving treatment or concomitant medications that could have a negative impact on the safety of patients enrolled or confound the results of the study.

- Population of interest is patients with moderate-to-severe plaque psoriasis per the protocol inclusion/exclusion criteria. Analysis populations are defined in Section [6.1.1](#). The analysis population corresponding to each of the efficacy and health outcome endpoints is specified in [Table RHCR 6.5](#) and [Table RHCR.6.7](#).
- Primary, major secondary, and exploratory endpoints/variables are listed in [Table RHCR.4.1](#). A full list of efficacy and health outcome endpoints/variables are given in [Table RHCR 6.4](#) and [Table RHCR.6.6](#).
- Population Level Summary: binary variables will be summarized by proportion and continuous variables will be summarized by average. Details are given in [Table RHCR 6.5](#) and [Table RHCR.6.7](#).
- Intercurrent Event(s) Strategy: intercurrent events will be handled by the composite strategy, the hypothetical strategy, or a combination of the composite and while-on-treatment strategies. Specific statistical methods to be used for handling intercurrent events under different strategies are described in Section [6.3](#). Statistical methods corresponding to each of efficacy and health outcome variables are summarized in [Table RHCR 6.5](#) and [Table RHCR.6.7](#).

Table RHCR.4.1. Objectives and Endpoints

Objectives	Endpoints

Primary To assess whether ixekizumab is superior to guselkumab at Week 12 in the treatment of patients with moderate-to-severe plaque psoriasis, as measured by PASI 100
	
 • Proportion of patients achieving PASI 100 at Week 12

Major Secondary To assess whether ixekizumab is superior to guselkumab in the treatment of patients with moderate-to-severe plaque psoriasis at different time points, as measured by:
 
 • PASI 75 • PASI 90 • PASI 100 • sPGA (0) • PASI 50 	
 • Proportion of patients achieving PASI 75 at Week 2 • Proportion of patients achieving PASI 90 at Weeks 4 and 8 • Proportion of patients achieving PASI 100 at Weeks 4, 8, 24 • Proportion of patients achieving sPGA (0) at Week 12 • Proportion of patients achieving PASI 50 at Week 1

Exploratory To assess whether ixekizumab is superior to guselkumab in the treatment of patients with moderate-to-severe plaque psoriasis at different time points, as measured by:
 
 • sPGA (0, 1) • Itch NRS • Skin Pain VAS • DLQI (0,1) 
To assess whether ixekizumab is non-inferior
	
 • The proportion of patients with a static sPGA (0,1) at Weeks 4, 8, 12, 24 • The proportion of patients achieving the Itch NRS Responder definition at Weeks 4, 8, 12, and 24 (restricted to those patients with Itch NRS score ≥ 4 at baseline) • Change from baseline in Itch NRS score at Weeks 4, 8, 12, and 24 • The proportion of patients achieving Itch NRS (0) at Weeks 4, 8, 12, and 24 (restricted to those patients with Itch NRS score >0 at baseline). • The proportion of patients achieving Skin Pain VAS (0) at Weeks 4, 8, 12, and 24 (restricted to those patients with Skin Pain VAS >0 at baseline) • Change from baseline in Skin Pain VAS score at Weeks 4, 8, 12, and 24 • The proportion of patients achieving DLQI (0,1) at Weeks 2, 4, 8, 12, and 24

Objectives	Endpoints
to guselkumab in the treatment of patients with moderate-to-severe plaque psoriasis at Week 24, as measured by: 
 • PASI 100 	
 • Proportion of patients achieving PASI 100 at Week 24

Abbreviations: DLQI = Dermatology Life Quality Index; NRS = Numeric Rating Scale; PASI = Psoriasis Area and Severity Index score; sPGA = static Physician Global Assessment; VAS = visual analog scale.

5. Study Design

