
 
• Skin Pain VAS                             
 
○ Skin Pain VAS (0)
 
○ Change from baseline
 
 
 
	
 
○ The proportion of patients achieving Skin Pain VAS (0) at Weeks 4, 8, 12, and 24 (restricted to those patients with Skin Pain VAS score >0 at baseline)
 
○ Change from baseline in Skin Pain VAS score at Weeks 4, 8, 12, and 24
 

 
• DLQI (0,1)
 
	
 
• The proportion of patients achieving DLQI (0,1) at Weeks 2, 4, 8, 12, and 24 (restricted to those patients with DLQI score >1 at baseline)
 

[figure not shown]
Abbreviations: DLQI = Dermatology Life Quality Index; NRS = Numeric Rating Scale; PASI = Psoriasis Area and Severity Index; Ps = plaque psoriasis; sPGA = static Physician Global Assessment; VAS = visual analog scale.

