## 5.2. Number of Participants

Approximately 1300 participants will be screened to achieve 960 randomized participants (480 randomized participants per treatment group). Based on experience from the previous UNCOVER-1, -2, -3, and IXORA-S trials, a 5% dropout rate is anticipated.

Patients with previous biologic use can be included in the study provided all inclusion/exclusion criteria, including the washout period(s), as specified in Sections 6.1 and 6.2 of this protocol are respected. Patients with previous exposure to another IL-17 antagonist(s) will be limited to approximately 15% of the total patient population.

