Previous phototherapy (UVB or PUVA)	No	Never used, PUVA only, UVB only, PUVA and UVB	X
Prior biologic failure ⁱ within prior biologic exposures	No	Not exposed, Exposed but not failed, Exposed and failed	X
Prior systemic failure ⁱ	No	Failed, Not failed	X

Patient Characteristics and Variables for Subgroup Analysis

Variable ^a	Quantitative Summary	Categorical Summary	Subgroup Analysis ^b
Psoriasis Duration and Age at Diagnosis			
Duration of psoriasis diagnosis (years) ^j	Yes	<5 years, 5 to <10 years, 10 to <20 years, ≥20 years	
Age at psoriasis diagnosis (years) ^k	Yes	<25, ≥25	
		<40, ≥40	
Baseline Disease Severity			
Baseline PASI	Yes	<20, ≥20	X
		<15, ≥15	
Baseline sPGA	No	3, 4, 5	X
Baseline BSA (%)	Yes	<20%, ≥20%	X
Baseline PGA-F	No	0, 1, 2, 3, 4	
		< 3, ≥3	X
Baseline Itch NRS	Yes	<4, ≥4	
		=0, >0	
Baseline DLQI	Yes	<5, ≥5	
		<11, ≥11	
Baseline Skin Pain VAS	Yes	=0, >0	
Baseline PatGA	No	0, 1, 2, 3, 4, 5	
Psoriatic arthritis at baseline	No	Yes, No	X
Baseline patient's global assessment of disease activity VAS for patients with baseline psoriatic arthritis	Yes	None	
Baseline patient's assessment of pain VAS for patients with baseline psoriatic arthritis	Yes	None	
Baseline physician's global assessment of disease activity VAS for patients with baseline psoriatic arthritis	Yes	None	

Abbreviations: BMI = body mass index; BSA = body surface area; DLQI = Dermatology Life Quality Index; eCRF = electronic case report form; IL-17 = interleukin-17; NRS = Numeric Rating Scale; PASI = Psoriasis Area and Severity Index; PGA-F = Physician's Global Assessment of Fingernail Psoriasis; PUVA = psoralen ultraviolet A; sPGA = static Physician Global Assessment; TNF = tumor necrosis factor; UVB = ultraviolet B; VAS = visual analog scale.

^a Refer to Sections 6.10 and 6.11 for variable abbreviation.

^b Subgroup analysis will be used for efficacy endpoints only. See Section 6.16.1 for more details.

^c Age (in years) will be calculated as length of the time interval from the imputed date of birth (July 1st in the year of birth collected in the eCRF) to the date that the patient was randomized.

^d BMI will be calculated as: $BMI (kg / m^2) = Weight (kg) / (Height (m))^2$.

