		DLQI daily activities domain	Sum of responses of questions #3 and #4: #3. How much has your skin interfered with you going shopping or looking after your home or garden? #4. How much has your skin influenced the clothes you wear?	If one question in a domain is missing, that domain is missing.
		DLQI leisure domain	Sum of responses of questions #5 and #6: #5. How much has your skin affected any social or leisure activities? #6. How much has your skin make it difficult for you to do any sport?	If one question in a domain is missing, that domain is missing.
		DLQI work and school	Sum of responses of questions question #7A and #7B:	If the answer to question

Measure	Description	Variable	Derivation / Comment	Handling of Missing Components
	period of this scale is over the “last week”. Response categories and corresponding scores are: Very much = 3 A lot = 2 A little = 1 Not at all = 0 Not relevant = 0	domain	#7A. Has your skin prevented you from working or studying? #7B. If No: how much has your skin been a problem at work or studying?	#7A is missing, this domain is missing. If #7A is No, and #7B is missing, this domain is missing.
		DLQI personal relationships domain	Sum of responses of questions #8 and #9: #8. How much has your skin created problems with your partner or any of your close friends or relatives? #9. How much has your skin caused any sexual difficulties?	If one question in a domain is missing, that domain is missing.
		DLQI treatment	Response of question #10: #10. How much of a problem has the treatment for your skin been, for example by making your home messy, or by taking up time?	If one question in a domain is missing, that domain is missing.
		DLQI total score	A DLQI total score is calculated by summing all 10 question responses, and has a range of 0 to 30 (less to more impairment) (Finlay and Khan 1994; Basra et al. 2008).	If two or more questions are missing, the total score is missing. Note: #7B could be a valid missing while #7A is not “No.” That is, #7 should be considered as one question.
		DLQI (0,1)	A DLQI (0,1) response is defined as a post-baseline DLQI total score of 0 or 1. A DLQI total score of 0 to 1 is considered as having no effect on a patient’s HRQoL (Khilji et al. 2002; Hongbo et al. 2005).	Missing if DLQI total score is missing
		DLQI (0)	A DLQI (0) response is defined as a post-baseline DLQI total score of 0.	Missing if DLQI total score is missing

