	Itch NRS ≥ 4 improvement from baseline	CMH test with NRI; Fisher’s Exact test with NRI	ITT Population - with baseline Itch NRS Score ≥ 4	IXE vs. GUS at all post-baseline visits	Exploratory analysis (Section 6.11.3).
	Itch NRS = 0	CMH test with NRI; Fisher’s Exact test with NRI	ITT Population - with Baseline Itch NRS Score > 0	IXE vs. GUS at all post-baseline visits	Exploratory analysis (Section 6.11.3).
DLQI	DLQI total score and domain scores change from baseline	MMRM; ANCOVA with mBOCF for the Blinded Treatment Periods	ITT Population	IXE vs. GUS at all post-baseline visits	Exploratory analysis (Section 6.11.3).
	DLQI ≥ 5 improvement from baseline	CMH test with NRI; Fisher’s Exact test with NRI	ITT Population with Baseline DLQI ≥ 5	IXE vs. GUS at all post-baseline visits	Exploratory analysis (Section 6.11.3).
	DLQI (0, 1)	CMH test with NRI; Fisher’s Exact test with NRI	ITT Population	IXE vs. GUS at all post-baseline visits	Exploratory analysis (Section 6.11.3).
Skin Pain VAS	Skin Pain VAS change from baseline	MMRM; ANCOVA with mBOCF for the Blinded Treatment Periods	ITT Population	IXE vs. GUS at all post-baseline visits	Exploratory analysis (Section 6.11.3).
	Skin Pain VAS = 0	CMH test with NRI; Fisher’s Exact test with NRI	ITT Population – with baseline Skin Pain VAS > 0	IXE vs. GUS at all post-baseline visits	Exploratory analysis (Section 6.11.3).
Patient’s Global Assessment of Disease Severity (PatGA)	PatGA (0)	CMH test with NRI; Fisher’s Exact test with NRI	ITT Population	IXE vs. GUS at all post-baseline visits	Exploratory analysis (Section 6.11.3).
	PatGA (0, 1)	CMH test with NRI; Fisher’s Exact test with NRI	ITT Population	IXE vs. GUS at all post-baseline visits	Exploratory analysis (Section 6.11.3).
	PatGA ≥ 2 improvement from baseline	CMH test with NRI; Fisher’s Exact test with NRI	ITT Population with Baseline PatGA ≥ 2	IXE vs. GUS at all post-baseline visits	Exploratory analysis (Section 6.11.3).

Measure	Variable	Analysis Method (Sections 6.1.3 and 6.3)	Analysis Population (Section 6.1.1)	Comparison / Time Point	Analysis Type
Patient's Assessment of Pain VAS	Patient's Pain VAS change from baseline; percent improvement	ANCOVA with mBOCF; MMRM for the Blinded Treatment Periods	ITT Population – with psoriatic arthritis at baseline	IXE vs. GUS at all post-baseline visits	Exploratory analysis (Section 6.11.3).

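### The SAP drops the protocol's baseline DLQI >1 restriction from the exploratory DLQI (0,1) endpoint, and its baseline table would not show how many patients this adds

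*SAP*

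**What the plan says.** **Protocol, Section 4, Table RHCR.4.1.** The exploratory endpoint is the proportion reaching DLQI (0,1) at Weeks 2, 4, 8, 12 and 24, "restricted to those patients with DLQI score >1 at baseline".

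**SAP, Section 4, Table RHCR.4.1.** The same endpoint and weeks appear as "The proportion of patients achieving DLQI (0,1) at Weeks 2, 4, 8, 12, and 24", without the condition.

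**SAP, Section 4, estimand text.** "The analysis population corresponding to each of the efficacy and health outcome endpoints is specified in" Tables RHCR 6.5 and RHCR.6.7, so those tables govern the population.

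**SAP, Section 6.12, Table RHCR.6.7.** The row reads "DLQI (0, 1) CMH test with NRI; Fisher’s Exact test with NRI ITT Population", with no baseline condition.

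**SAP, Section 6.12, Table RHCR.6.6.** "A DLQI (0,1) response is defined as a post-baseline DLQI total score of 0 or 1". The baseline score plays no part.

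**SAP, Section 6.7.1, Table RHCR.6.3.** Baseline DLQI has a quantitative summary and two categorical splits, at 5 and at 11. There is no split at 1.

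**The concern.** The restriction belongs to the protocol's endpoint definition. It ensures that reaching 0 or 1 means a change from a worse score. The entry criteria set minimum sPGA, PASI and BSA values but no minimum DLQI, so patients at 0 or 1 can be randomized. Under the SAP, such a patient counts as a responder by staying where they started.

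The pattern looks more like an omission than a decision. The protocol restricts four exploratory endpoints by baseline score: Itch NRS responder, Itch NRS (0), Skin Pain VAS (0) and DLQI (0,1). The SAP keeps the first three and loses only the fourth. It also restricts its own endpoint of a DLQI improvement of at least 5 points to patients with baseline DLQI of at least 5. PatGA (0) and (0,1) are unrestricted too, but the protocol sets no condition for them.

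Table RHCR.6.3 has baseline categories matching the three kept restrictions (Itch below 4 or not, Itch 0 or above, Skin Pain 0 or above). It has none at DLQI 1, so a reader of that table could not see how many patients the wider population brings in.

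**Working it through.** The plan states no response rate, power or expected baseline distribution for this endpoint, so there is no figure to reproduce. The check is a comparison of texts, followed by an illustration of size on stated assumptions.

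**1. Texts side by side**

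| Item | Protocol | SAP |
|---|---|---|
| Population for DLQI (0,1) | Baseline DLQI >1 | ITT, no condition (Tables RHCR.4.1 and RHCR.6.7) |
| Itch NRS responder | Baseline ≥4 | Baseline ≥4 |
| Itch NRS (0) | Baseline >0 | Baseline >0 |
| Skin Pain VAS (0) | Baseline >0 | Baseline >0 |

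The SAP's tables agree with one another on DLQI (0,1), so a programmer following it would include every randomized patient.

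**2. Inputs for the size**

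- 480 patients per arm, 960 in total (SAP Section 5.3).
- q, the share with baseline DLQI 0 or 1: not in the documents. Assumed 2%, 5% or 10%, which is about 19, 48 or 96 of 960.
- r, the share of those patients counted as responders: assumed 95% in each arm. Protocol Section 5.2 says "a 5% dropout rate is anticipated". Dropouts are scored as nonresponders, and everyone retained is assumed to be still at 0 or 1.
- Response among patients with baseline DLQI >1: assumed 60% for ixekizumab and 50% for guselkumab, so d = 10 points.

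**3. Reported rates and difference**

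Reported rate = q × r + (1 − q) × p.

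Reported difference = (1 − q) × d + q × d₀, where d₀ is the between-arm difference among patients starting at 0 or 1. With equal r in both arms, d₀ = 0 and the difference is (1 − q) × d.

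- q = 2%: 1.9 + 58.8 = 60.7 vs 1.9 + 49.0 = 50.9; difference 9.8.
- q = 5%: 4.75 + 57.0 = 61.75 vs 4.75 + 47.5 = 52.25; difference 9.5.
- q = 10%: 9.5 + 54.0 = 63.5 vs 9.5 + 45.0 = 54.5; difference 9.0.

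The choice of r moves the rates but not the difference. At q = 10%, r = 100% gives 64.0 vs 55.0 and r = 80% gives 62.0 vs 53.0, both 9.0 points apart. If d₀ = d, the difference does not shrink.

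**4. Does the larger population buy power?**

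Two-sided 0.05, normal approximation, n per arm:

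Power = Φ{ [ d√n − 1.96 √(2 p̄(1 − p̄)) ] / √( p₁(1 − p₁) + p₂(1 − p₂) ) }

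Unrestricted at q = 5%: n = 480, rates 0.6175 and 0.5225, p̄ = 0.57. The numerator is 0.095 × 21.91 − 1.96 × 0.700 = 0.709, the denominator is 0.697, the ratio is 1.02 and power is 84.6%.

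Restricted at q = 5%: n = 456, rates 0.60 and 0.50, p̄ = 0.55. The numerator is 0.10 × 21.35 − 1.96 × 0.704 = 0.756, the denominator is 0.700, the ratio is 1.08 and power is 86.0%.

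| q | Reported rates | Difference | Power, unrestricted (480 per arm) | Power, restricted (n per arm) |
|---|---|---|---|---|
| 2% | 60.7 vs 50.9 | 9.8 | 86.5% | 87.0% (470) |
| 5% | 61.8 vs 52.3 | 9.5 | 84.6% | 86.0% (456) |
| 10% | 63.5 vs 54.5 | 9.0 | 81.0% | 84.1% (432) |

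Under these assumptions the restricted analysis has slightly more power despite fewer patients.

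**The case against.** **The protocol allows such changes.** Protocol Section 10.3.3.3 leaves analysis details of exploratory endpoints to the SAP. Section 10.3.1 requires an amendment only for a principal feature, with other method changes justified in the study report. So no amendment is needed, and a missing reason in the SAP is not in itself a breach. But Section 10.3.3.3 refers to the endpoints as listed in Table RHCR.4.1, where the restriction is part of the definition, and the SAP does not flag that it has altered one.

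**The count can be recovered.** Under protocol Section 10.3.1, continuous summaries include the minimum. A minimum of 2 or more would show that nobody with a recorded baseline starts at 0 or 1. The category below 5 gives an upper bound, and SAP Section 6.7.1 plans by-patient listings. All true. The gap is only that the table does not give the count.

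**It may be deliberate.** The SAP also drops the protocol's 2-point improvement condition from exploratory sPGA (0,1). That condition is redundant for patients who enter with sPGA of at least 3. The DLQI restriction is redundant only if no one starts at 0 or 1. The documents do not settle intent, which is why justifying the change is an acceptable alternative to reversing it.

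**The effect may be negligible, and it does not favour the sponsor.** Entry requires extensive skin disease, so q could be near zero; at q = 2% the difference moves 0.2 points. If the added patients respond equally in both arms, the change dilutes the difference and works against the superiority objective. This stands and limits the weight of the point, but the mismatch remains.

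**Conclusion.** The concern holds, at minor weight. Followed as written, the SAP reports DLQI (0,1) in a different population from the one the protocol specifies, gives no reason, and plans no tabulated count of the patients who make the difference.

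The size depends on q, which is unknown. With 2% to 10% of patients at baseline 0 or 1, equal response among them in both arms, and assumed rates of 60% vs 50% in the rest, the reported difference falls by 0.2 to 1.0 point and both arms' rates rise (at q = 10%, by 3.5 and 4.5 points). If there are no such patients, or if they show the same between-arm difference as the rest, the difference does not shrink. No bias toward one arm is implied. The endpoint is exploratory and has no multiplicity adjustment. PASI 100 at Week 12 and the other sequentially tested endpoints are untouched.

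**What to change.** 1. In SAP Table RHCR.4.1 and the DLQI (0, 1) row of Table RHCR.6.7, set the population to ITT patients with baseline DLQI >1. Keep the unrestricted ITT result as a labelled supplementary row.
2. Alternatively, if the unrestricted version is meant as the main analysis, say so in the SAP with the reason, and report the protocol's restricted version beside it.
3. In either case, add the categories ≤1 and >1 to the baseline DLQI row of Table RHCR.6.3.
4. Optionally, state whether the same condition applies to DLQI (0,1) in the AUC analysis of SAP Section 6.11.3, and likewise for itch NRS (0). That analysis appears only in the SAP, so this is for consistency and restores no protocol text.

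The cost is SAP wording, one subset flag and one baseline category. The restricted analysis would have about 10 to 48 fewer patients per arm if q is 2% to 10% (480 × 0.02 ≈ 10; 480 × 0.10 = 48).
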